## 1. SYNOPSIS

Name of Sponsor/Company: Mineralflys Therapeutics, Inc.	
Name of Investigational Product: MLS-101: [REDACTED] [REDACTED]	
Name of Active Ingredient: MLS-101	
Title of Study: A Randomized, Double-blind, Placebo-controlled, Dose-ranging, Multicenter Phase 2 Study to Evaluate the Safety, Efficacy, and Tolerability of MLS-101 in Subjects With Uncontrolled Hypertension	
Number of Study Center(s): Approximately 50 centers in the United States for Part 1 and approximately 10 centers in the United States for Part 2	
Study Period: Date first subject enrolled: 30 July 2021 Estimated date last subject last visit: Q3 2022	Phase of Development: Phase 2
Objectives and Endpoints: Objectives: Primary: 

To characterize the effect of MLS-101 on blood pressure (BP) at 5 dosing regimens versus placebo when administered orally for the treatment of uncontrolled hypertension as add-on therapy to stable background treatment

 Secondary: 

To investigate the safety and tolerability of MLS-101 at 5 dosing regimens versus placebo when administered orally for the treatment of uncontrolled hypertension as add-on therapy to stable background treatment

To investigate the pharmacokinetic (PK) profile of MLS-101 at 5 dosing regimens when administered orally for the treatment of uncontrolled hypertension as add-on therapy to stable background treatment

To investigate the pharmacodynamic (PD) parameters of MLS-101 at 5 dosing regimens when administered orally for the treatment of uncontrolled hypertension as add-on therapy to stable background treatment

 Endpoints: Efficacy Primary: 

Change in office-measured (average of last 2 of 5 unattended measurements using an automated oscillometric sphygmomanometer device after approximately 5 minutes of rest in the seated position) systolic blood pressure (SBP) from baseline to the end of Study Week 8 (ie, Study Day <math>56 \pm 2</math> or end-of-treatment period)

 Secondary: 

Change in 24-hour ambulatory blood pressure monitoring (ABPM) parameters (systolic and diastolic) from baseline to the end of Study Week 7 (ie, Study Day <math>49 \pm 2</math>)

	

- Change in office-measured (average of last 2 of 5 unattended measurements using an automated oscillometric sphygmomanometer device after approximately 5 minutes of rest in the seated position) SBP and diastolic blood pressure (DBP) from baseline to the end of Study Weeks 1, 2, 3, 4, 5, 6 and 7 ( $\pm 2$  days); change in office-measured DBP from baseline to the end of Study Week 8 (ie, Study Day  $56 \pm 2$  or end-of-treatment period)
- Proportion of subjects who achieve office-measured BP of  $\leq 130/80$  mmHg by the end of Study Week 8 (ie, Study Day  $56 \pm 2$  or end-of-treatment period)

#### *Safety*

- Incidence and severity of all spontaneously reported adverse events (AEs)
- Changes in vital signs (SBP, DBP, body temperature, heart rate, and respiratory rate)
- Changes in electrocardiogram parameters (including cardiac intervals: PR, QRS, QT, and corrected QT interval using Fridericia's formula)
- Changes in clinical laboratory assessments (hematology, chemistry, coagulation, and urinalysis)
- Change in office-measured SBP from Study Week 8 (end-of-treatment period) to Study Week 12 for Part 1 and Study Week 10 for Part 2 (end of follow-up)

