Subjects will orally administer the assigned study drug (MLS-101 or placebo) according to the assigned dosing regimen for 8 weeks beginning on Study Day 1. All subjects in Part 1 (regardless of dosing group) will receive BID dosing to preserve the integrity of the blind; active drug is administered as the morning dose for all QD dose groups. All subjects in Part 2 will receive QD dosing to be administered in the morning. Subjects will return to the research facility or be seen by the clinical investigator or approved home health care professional at the end of Study Weeks 1, 2, 3, 4, 5, 6, 7, and 8 ( $\pm$  2 days) for protocol-defined efficacy and safety assessments and procedures, assessment of AEs, and confirmation of compliance with study drug usage. Subjects will also complete a telephone visit and BP check at home approximately 3 days post last dose of study drug. Subjects will attend up to 14 full clinic visits, including a pre-Screening visit, a Screening/start of Placebo Run-in visit, a second visit during Placebo Run-in, a clinic visit to initiate the ABPM procedure, a Randomization visit, 8 weekly visits during double-blind treatment, and an end-of-study visit scheduled 4 weeks after the last study treatment in Part 1 and 2 weeks after the last study treatment in Part 2 for final efficacy and safety assessments. Subjects should be in a fasted state for all study visits in Part 2 unless there is a medical reason not to fast as determined by the investigator.

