#### **Safety Criteria for Dose Adjustment or Stopping Treatment:**

If, at any time during the study, a subject meets 1 or more of the clinical or laboratory exclusion criteria for the study (eg, seated SBP  $\geq$  175 mmHg or DBP  $\geq$  100 mmHg, serum potassium  $>$  5.2 mEq/L, serum cortisol  $<$  3 mcg/dL), laboratory test values will be confirmed using a local lab and BP measurements will be repeated. If laboratory exclusion criteria are met, the subject's dose of study drug may be temporarily withheld, adjusted, or stopped by the investigator in consultation with the medical monitor. The subject will receive appropriate antihypertensive treatment if clinically

indicated, and will remain in the study for further safety monitoring. Guidelines for dose adjustment/stopping in the management of hyperkalemia are included in [Section 6.5.1](#). All subjects will be given dietary counseling to avoid foods high in potassium during the study ([Appendix 12.6](#)). Guidelines for the management of hypotension are included in [Section 6.5.2](#). In addition, serum cortisol levels will be monitored throughout the study, and all subjects will be monitored for signs and symptoms of adrenal insufficiency (ie, nausea, vomiting, light-headedness, low BP, or electrolyte abnormalities) at every study visit. Based on changes in cortisol levels, an adrenocorticotrophic hormone (ACTH) stimulation test ([Appendix 12.7](#)) may be performed and the subject's dose of study drug may be stopped. Guidelines for potential dose discontinuation in the management of adrenal insufficiency are included in [Section 6.5.3](#).

Subjects who wish to stop treatment for any reason may stop at any time during the study. If the study treatment is permanently discontinued, the subject will remain in the study to complete all study assessments as described in the schedule of assessments (SoA) ([Table 1](#) and Table 2) through Study Week 8 (end-of-treatment visit). Subjects should also be encouraged to return for a final follow-up visit 4 weeks after the Study Week 8 visit for Part 1 and 2 weeks after the Study Week 8 visit for Part 2, at which the end-of-study assessments will be performed.

An overview of the study design is presented in the Study Schema ([Figure 1](#)). Safety and efficacy assessments and study procedures are outlined in the SoA ([Table 1](#) and Table 2). Detailed descriptions of study assessments are provided in [Section 4.8](#) and [Section 8](#).

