5.5 Visit Windows

No analysis visit windowing will be performed for this study with the exception of early termination visits (specifically the End of Treatment visit, which is recorded on the eCRF as Week 8/EOT). Early termination assessments will be re-numbered to an analysis visit based on their windowed visits defined by actual study day (see table below).

For the supplemental Estimand (defined in Section 6.4.1.5) only, post-treatment visits will also be re-numbered based on their windowed visits defined by actual study day. Specially, this refers to the End of Study visit at Week 12 (Part 1) or Week 10 (Part 2). This is because the supplemental

Estimand uses all observed data, regardless of whether they are on treatment or not. As the supplemental Estimand is only defined for SBP, this is the only variable for which the EOS visit windowing needs to be applied.

The following analysis visit windows will apply to early termination visits:

| Visit | Target Study Day | Analysis Window |
|--------------------|--------------------|--|
| Baseline | Day 1 | ≤ Day of first dose in Double-blind treatment period |
| Week 1 – Visit 7 | Day 7 (± 2) | Day 2 – Day 10 |
| Week 2 – Visit 8 | Day 14 (± 2) | Day 11 – Day 17 |
| Week 3 – Visit 9 | Day 21 (± 2) | Day 18 – Day 24 |
| Week 4 – Visit 10 | Day 28 (± 2) | Day 25 – Day 31 |
| Week 5 – Visit 11 | Day 35 (± 2) | Day 32 – Day 38 |
| Week 6 – Visit 12 | Day 42 (± 2) | Day 39 – Day 45 |
| Week 7 – Visit 13 | Day 49 (± 2) | Day 46 – Day 52 |
| Week 8 – Visit 14 | Day 56 (± 2) | ≥ Day 53 |
| Week 9 – Visit 15 | 3 days post EOS | N/A |
| Week 12 – Visit 16 | Day 84 (± 2) | N/A |

If more than one assessment occurs within a single visit window, the analysis will take the nominal visit assessment if there is a nominal visit or the later assessment if there is no nominal visit assessment.

For by-visit summaries, endpoints will be analyzed according to the nominal visits (i.e. assigned visit). Unscheduled measurements will not be included in by-visit summaries but will contribute to the Baseline timepoint and/or minimum/maximum/worst value (e.g. shift table), if applicable.

Listings will include all visit data, including unscheduled visits, in chronological order based on visit date.

[figure not shown]

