6.4.3.1 Change in SBP from End of Treatment to End of Study

Analysis of change in office-measured SBP from End of Treatment (Study Week 8 or last measurement prior to starting the rescue medication) to End of Study (Study Week 12 for Part 1 and Study Week 10 for Part 2) will be analyzed using an ANCOVA model with treatment group as a factor and SBP at EOT as a covariate.

A least-square estimate, along with the 90% CI, of the mean difference between each dose group and the placebo group will be provided for each time point. P-values corresponding to the pairwise tests, not adjusted for multiplicity, of the difference between each dose group vs placebo will also be provided.

6.4.3.2 Comparison between 100mg QD and 25mg BID in Change from Baseline to Week 8 in SBP

Subjects randomized to 100mg QD in Part 1 and 2 and 25 BID dose in Part 1 will be included in this analysis.

The two dose levels, 100mg QD and 25mg BID will be tested for the equality of distributions using Kolmogorov-Smirnov test. If the distributions of responses are considered comparable across dose

and PRA levels at baseline, the dose groups will be pooled. This dataset will be used to repeat efficacy analyses, including the primary and select subset analyses.

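### The off-treatment SBP change starts at Study Week 8 even for subjects who stopped study drug earlier without rescue, which pulls the estimated rise toward zero

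*Protocol*

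**What the plan says.** Among the safety endpoints (Protocol Synopsis and 3.2.3), the protocol lists "Change in office-measured SBP from Study Week 8 (end-of-treatment period) to Study Week 12 for Part 1 and Study Week 10 for Part 2". SAP 3.4 repeats it. SAP 6.4.3.1 analyses it by ANCOVA, with treatment group as a factor and SBP at end of treatment as a covariate. It reports 90% confidence intervals and p-values for each dose against placebo, and sets the start value as "End of Treatment (Study Week 8 or last measurement prior to starting the rescue medication").

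For subjects who stop drug for good, the protocol (Synopsis, Safety Criteria; repeated in 4.1 and 7.1) says: "If the study treatment is permanently discontinued, the subject will remain in the study to complete all study assessments", and this runs "through Study Week 8 (end-of-treatment visit"). They are then encouraged to "return for a final follow-up visit 4 weeks after the Study Week 8 visit for Part 1", or 2 weeks after it in Part 2. SAP 5.4 likewise follows subjects who withdraw from treatment to End of Study.

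SAP 5.5 deals with a Week 8/EOT page completed early: "Early termination assessments will be re-numbered to an analysis visit based on their windowed visits defined by actual study day". Only readings from Day 53 onward fall in the Week 8 window.

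**The concern.** The endpoint is meant to show what happens to SBP once MLS-101 is withdrawn, so its start value should be an on-drug reading. For completers it is: Protocol 4.8.13 takes the Week 8 office reading before that day's dose. For someone who stopped in, say, Week 2 and was not rescued, the Week 8 reading is labelled end of treatment but comes weeks after the last dose. The change to End of Study then runs from off drug to off drug and carries little or no information about withdrawal.

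The SAP re-anchors subjects whose Week 8 value is affected by rescue, but has no matching rule for subjects whose Week 8 value is affected by stopping drug. At stake is an understated rise after treatment, carried into the dose-versus-placebo estimates of SAP 6.4.3.1.

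**Working it through.** **1. Which value starts the change, by type of subject**

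- Completer, no rescue: Week 8 reading, on drug.
- Rescue started: last reading before rescue (SAP 6.4.3.1).
- Early stop, no rescue, attends Week 8: Week 8 reading, off drug.
- Early stop, no rescue, EOT visit done at drug stop, no later Week 8 reading: SAP 5.5 renumbers the visit by study day. A Day 14 visit, for example, falls in the Week 2 window (Days 11 to 17). The subject may then have no Week 8 start value. That is missing data, not a zero change.

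No other rule fills the gap. The baseline imputation for treatment-related withdrawal in SAP 6.4.1.1 belongs to the primary estimand and would not supply an on-drug value anyway. Protocol 6.3 sends unblinded subjects to end-of-treatment assessments after stopping, without saying how that reading enters this endpoint.

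**2. Planning figure**

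The Synopsis gives 30 per arm, SD 9 and a 90% two-sided interval. Half-width = 1.645 × 9 × √(2/30) = 3.82, which reproduces the stated ±3.8. That figure is for change from baseline; the documents give none for the off-treatment change.

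**3. Dilution of the mean rise**

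Assumptions: the true rise after stopping equals the planning effect of 10 mmHg (Synopsis), and a share p of the arm stopped early without rescue and attends Week 8. If a fraction f of the effect is already lost by Week 8 in those subjects, and the rest by End of Study, then

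mean observed rise = 10 × (1 − p × f).

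With f = 1:

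- p = 0.05: 10 × 0.95 = 9.5 (loss 0.5)
- p = 0.10: 10 × 0.90 = 9.0 (loss 1.0)
- p = 0.20: 10 × 0.80 = 8.0 (loss 2.0)

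In an arm of 30 these shares are 1.5, 3 and 6 subjects. With f = 0.5, as for subjects who stop shortly before Week 8, each loss halves. Neither p nor f is in the documents.

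**4. Does the planned ANCOVA remove it?**

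This was simulated with 400,000 per arm, a 10 mmHg rise, SD of change 9, early stoppers in the active arm only, f = 1, and the SD of SBP at each visit assumed to be 10, 12 or 15. Treatment difference in mmHg:

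| Visit SD | p = 0 | p = 0.05 | p = 0.10 | p = 0.20 |
|---|---|---|---|---|
| 10 | 6.0 | 5.5 | 5.1 | 4.4 |
| 12 | 7.2 | 6.7 | 6.3 | 5.5 |
| 15 | 8.2 | 7.7 | 7.2 | 6.4 |

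The p = 0 column is below 10 because the model adjusts for SBP at end of treatment, which treatment itself affects; that is a separate matter. Reading across each row, the loss from early stoppers remains and is close to that in the raw means.

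**The case against.** A change between two fixed visits, Week 8 to Week 12 (Week 10 in Part 2), is a legitimate definition. It gives every subject the same interval, whereas a last-on-drug start compares unequal ones. In Part 1, a subject who stops on Day 14 would be 84 − 14 = 70 days off drug at End of Study, against 84 − 56 = 28 for a completer. The affected group may also be small: under SAP 6.7.6, an early stopper who starts another antihypertensive by the Week 8 office reading counts as rescued and leaves it. The size is assumed throughout. Even at 20% early stoppers, the 2.0 mmHg loss is smaller than the ±3.8 half-width. The study is exploratory and the endpoint is a safety one.

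Most of this stands and limits the weight of the point. It does not remove it. A fixed-visit definition is coherent only if Week 8 is not also presented as the end of treatment, and the SAP has already left that definition for rescued subjects. The loss is a systematic shift, which the confidence interval does not reflect. The unequal interval is a real cost of the remedy and has to be shown.

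**Conclusion.** The point holds for subjects who permanently stop study drug before Week 8 without starting rescue. Under the stated rules, those who attend Week 8 contribute an off-drug start value and pull the estimated rise toward zero; those whose EOT visit was done at drug stop may have no start value. The loss is 0.5 to 2.0 mmHg on a 10 mmHg rise for 5% to 20% early stoppers, if the effect is fully lost by Week 8, and smaller otherwise. Only this safety and supportive endpoint is affected; the primary analysis is not.

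A reader might infer three stronger things that the documents do not support:

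- **That Week 8 is the start for everyone.** The rescue clause in SAP 6.4.3.1 contradicts this.
- **That End of Study is dated inconsistently for early stoppers.** Protocol Methodology speaks of "an end-of-study visit scheduled 4 weeks after the last study treatment in Part 1", which for a Day 14 stop would give Day 14 + 28 = 42 rather than 56 + 28 = 84. That sentence describes the planned 8-week course. The specific rule after early discontinuation is a "final follow-up visit 4 weeks after the Study Week 8 visit for Part 1". Protocol Table 1 and 4.8.16 fix the visit at Day 84, and SAP 6.4.3.1 uses Week 12.
- **That the bias is known to differ between arms.** Table 3 reaches a zero dose at the second reduction for 25 mg BID and 50 mg QD but not for 100 mg QD. However, Protocol 6.5.1 can lead to a hold or discontinuation in any arm, and no rates by arm are given.

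**What to change.** In SAP 6.4.3.1, define End of Treatment per subject as the last scheduled office BP reading taken while on study drug and before any rescue medication. For completers this is the Week 8 reading, so nothing changes for them. For this derivation, a subject at the zero level of Table 3 counts as off drug. Do not add a narrow tolerance around the last dose: readings are weekly, so a subject whose last dose is on Day 17, with visits on Days 14 and 21, would have no reading within 2 days.

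If the fixed Week 8 start is kept, the minimum is an added analysis limited to subjects still on study drug at the Week 8 reading. Either way, report days from last dose to End of Study by arm, and align the wording of SAP 3.4 and Protocol 3.2.3.

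The cost is SAP wording, one derivation and one summary. Weekly office readings (Protocol Tables 1 and 2) and drug stop dates (Protocol 6.4) are already collected. The downside is that, with a last-on-drug start, early stoppers have a longer off-drug interval than completers, which the days-off-drug summary must make visible.

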#### *Pharmacokinetics*

- PK parameters, including, if feasible, area under the plasma concentration versus time curve (AUC), maximum plasma concentration ( $C_{max}$ ), time to maximum concentration ( $T_{max}$ ), and half-life ( $t_{1/2}$ ) will be summarized descriptively for Randomization (baseline) and Study Weeks 1, 4, and 8

#### *Pharmacodynamics*

- Change in plasma 11-deoxycortisol and plasma renin activity (PRA) from baseline to the end of Study Weeks 4 and 12 for Part 1 and end of Study Weeks 4 and 10 for Part 2 (end of follow-up)
- Change in serum aldosterone, cortisol, and 11-deoxycorticosterone concentration from baseline to the end of Study Weeks 4 and 12 for Part 1 and end of Study Weeks 4 and 10 for Part 2 (end of follow-up)

#### **Methodology:**

This is a 2-part Phase 2 randomized, double-blind, placebo-controlled, dose-ranging, multicenter study designed to evaluate the effect of orally administered MLS-101 on BP for the treatment of uncontrolled hypertension (hypertensive despite receiving  $\geq 2$  antihypertensives) when used as add-on therapy to stable background treatment in male and female subjects  $\geq 18$  years of age. Stable background treatment must include  $\geq 2$  antihypertensives (note: a combination pill = 2 antihypertensives) that have been stable at their prescribed doses and stable for at least 4 weeks prior to signing the Screening/main study informed consent form (ICF). Background therapy may be adjusted at the investigator's discretion.

Subjects with a history consistent with inadequately controlled hypertension, (ie, SBP  $\geq 135$  mmHg on a stable treatment regimen of  $\geq 2$  antihypertensives), will undergo pre-Screening laboratory tests for PRA and aldosterone following their agreement to enter pre-Screening and completion of a pre-Screening ICF that has been approved by the Institutional Review Board (IRB). In Part 1 of the study, the value of PRA must be  $\leq 1$  ng/mL/h based on morning measurement. If the value of PRA  $> 1$  ng/mL/h based on morning measurement, then subjects may be eligible to enter Part 2 of the study. The value for aldosterone must be  $\geq 1$  ng/dL based on morning measurement for both Part 1 and Part 2. Alternative target PRA and/or aldosterone criteria for the study may be provided by the sponsor. These alternative targets may be adjusted during conduct of the trial based on ongoing review of PRA and serum aldosterone values. Subjects with PRA and serum aldosterone values meeting the stipulated guidance criteria will then enter the study Screening process. If PRA and/or

serum aldosterone do not meet the target guidance values during pre-Screening, the PRA and aldosterone measurements may be repeated 1 time and the pre-Screening window will reset to 2 weeks for Part 1 or 4 weeks for Part 2. If guidance criteria are revised, then previously pre-screened individuals who meet the revised criteria may be considered for entry into the Screening process with consent of the sponsor, and the pre-Screening window will reset to 2 weeks for Part 1 and 4 weeks for Part 2.

The current estimate is that approximately 1100 subjects will undergo up to 2 weeks of pre-Screening for Part 1 and 4 weeks of pre-Screening for Part 2. It is estimated that approximately 270 subjects will have qualifying PRA and serum aldosterone levels to be eligible to enter Screening/start of Placebo Run-in for Part 1 after completing a Screening/main study ICF that has been approved by the IRB. Assuming an approximately 40% screen failure rate, a total of approximately 160 subjects will meet all eligibility requirements to qualify for enrollment in Part 1 of the study. For Part 2, it is estimated that approximately 60 subjects will have qualifying PRA and serum aldosterone levels to be eligible to enter Screening/start of Placebo Run-in for Part 2 after completing a Screening/main study ICF that has been approved by the IRB. Assuming an approximately 40% screen failure rate, a total of 36 subjects will meet all eligibility requirements to qualify for enrollment in Part 2 of the study.

At the Screening/start of Placebo Run-in visit (V2/V3), subjects will complete the Screening assessments and begin a single-blind (subjects blinded to treatment allocation) run-in period (up to 2 weeks) of twice-daily (BID) oral treatment with placebo in Part 1 and once daily (QD) oral treatment with placebo in Part 2, while continuing to remain on stable doses of their background antihypertensive medications. Using an automated oscillometric sphygmomanometer device, SBP and DBP will be measured 5 times after approximately 5 minutes of rest in the seated position according to the American Heart Association (AHA) Guidelines ([Muntner 2019](#)). The average of the last 2 of 5 unattended measurements of SBP and DBP, respectively, will be used for the analysis. Subjects may also be provided with an automated digital oscillometric home BP device to measure BP at home at the investigator's discretion. In addition to sitting measurements, standing BP will be measured at the Screening/start of Placebo Run-in visit, Randomization, Study Week 1, and Study Week 8 with an automated office blood pressure (AOBP) device according to the procedure described in [Appendix 12.5](#). Subjects will return to the research facility at the start of Week 2 of the run-in period (V4) for protocol-defined assessments including BP measurements.

At the second clinic visit of the Placebo Run-in period, subjects will be evaluated for eligibility based on Screening data, and if eligible, will continue Week 2 of Placebo Run-in. Subjects will be given an ABPM device and instructions on how to perform the ABPM procedure at home by the investigator. The ABPM procedure will be initiated at home approximately 24 hours before Randomization (Study Day 1) and again in the clinic at the end of Study Week 4 (ie, Visit 10, Study Day  $28 \pm 2$ ) in Part 2 and Study Week 7 (ie, Visit 13; Study Day  $49 \pm 2$ ) in Parts 1 and 2. Alternatively, sites may choose to schedule an abbreviated office visit on Study Day 0 (Visit 5) to initiate the ABPM procedure. At the end of Study Weeks 4 and 7, the ABPM procedure can be initiated at home in extraordinary circumstances, such as site closure due to coronavirus disease 2019 (COVID-19), subject exposure to COVID-19, or subject testing positive for COVID-19. If, for any reason, the ABPM procedure is deemed a failure at the end of Study Week 7, it can be repeated at Study Week 8. In addition, subjects will be given either a spot urine collection kit for Part 1 or a 24-hour urine collection kit for Part 2 on the second visit of the placebo-run in period (Visit 4) to take home for use on Study Day 1. In Part 1 of the study, first morning urine will be collected prior to morning dose of study drug on Study Day 1 and again at the end of Study Week 8 (ie, Study Day  $56 \pm 2$  or end-of-treatment period) for determination of potassium, sodium, and creatinine levels. In Part 2 of the study, 24-hour urine collection will be performed on Study Day 1 and again at the end of Study Week 4 (ie, Visit 10, Study Day  $28 \pm 2$ ) for determination of potassium, sodium, creatinine, and aldosterone levels. After completion of the single-blind, Placebo Run-in period, subjects will participate in a telephone visit on Study Day 0 (Visit 5) in which they will be reminded of the instructions by the investigator or study

coordinator on how to perform the ABPM procedure and the spot/24-hour urine collection at home. Subjects will return to the clinic on Study Day 1, and those who continue to meet all eligibility requirements and complete all baseline procedures will be randomized to MLS-101 or placebo and undergo up to 8 weeks of treatment and either 4 weeks of follow-up in Part 1 or 2 weeks of follow-up in Part 2.

A planned interim analysis ([Section 9.5](#)) was conducted for Part 1 of the study and all available safety and tolerability data (vital signs, BP measurements, adverse events, and safety laboratory values) were reviewed by a Data and Safety Monitoring Board (DSMB) ([Section 8.3.8](#)). A second interim analysis at the end of Part 1 to review all available safety and tolerability data (vital signs, BP measurements, adverse events, and safety laboratory values) will be conducted. This analysis will also include Part 2 subjects that have completed week 4 at the time of data cut off. An additional interim analysis may be performed to support drug development decisions.

NOTE: In the previous version of the protocol, subjects in Part 1 of the study were randomized into 6 equal treatment groups (1:1:1:1:1:1) to 12.5 mg BID, 25 mg BID, 12.5 mg QD, 50 mg QD, 100 mg QD, or placebo. After a review of the clinical data at the December 2021 interim analysis, it was decided that the 2 lowest dose levels (12.5 mg QD and 12.5 mg BID) would be dropped due to lack of consistent meaningful reduction of blood pressure. Effective with Amendment 4, subjects will be randomized into 4 equal treatment groups (1:1:1:1) to 25 mg BID, 50 mg QD, 100 mg QD, or placebo.

For Part 1, approximately 120 of 160 enrolled subjects  $\geq$  18 years of age will be randomized into 4 equal treatment groups (1:1:1:1) to 25 mg BID, 50 mg QD, 100 mg QD, or placebo; each treatment group will consist of approximately 30 subjects stratified by BP (seated SBP  $\leq$  160 mmHg and seated SBP  $>$  160 mmHg). Approximately 40 of 160 enrolled subjects were enrolled and completed the study in the 2 low dose cohorts that were discontinued with Amendment 4 as described above.

For Part 2, approximately 36 enrolled subjects  $\geq$  18 years of age will be randomized (5:1) to either 100 mg QD MLS-101 or placebo such that the MLS-101 treatment group will consist of approximately 30 subjects and the placebo treatment group will consist of approximately 6 subjects.

Subjects will orally administer the assigned study drug (MLS-101 or placebo) according to the assigned dosing regimen for 8 weeks beginning on Study Day 1. All subjects in Part 1 (regardless of dosing group) will receive BID dosing to preserve the integrity of the blind; active drug is administered as the morning dose for all QD dose groups. All subjects in Part 2 will receive QD dosing to be administered in the morning. Subjects will return to the research facility or be seen by the clinical investigator or approved home health care professional at the end of Study Weeks 1, 2, 3, 4, 5, 6, 7, and 8 ( $\pm$  2 days) for protocol-defined efficacy and safety assessments and procedures, assessment of AEs, and confirmation of compliance with study drug usage. Subjects will also complete a telephone visit and BP check at home approximately 3 days post last dose of study drug. Subjects will attend up to 14 full clinic visits, including a pre-Screening visit, a Screening/start of Placebo Run-in visit, a second visit during Placebo Run-in, a clinic visit to initiate the ABPM procedure, a Randomization visit, 8 weekly visits during double-blind treatment, and an end-of-study visit scheduled 4 weeks after the last study treatment in Part 1 and 2 weeks after the last study treatment in Part 2 for final efficacy and safety assessments. Subjects should be in a fasted state for all study visits in Part 2 unless there is a medical reason not to fast as determined by the investigator.

